9.4.2.1 Additional efficacy analyses: longitudinal analysis of outcomes

The following will be used as sensitivity analyses.

Longitudinal analysis will examine the primary and secondary outcomes that are longitudinally collected at baseline and at 6, 12, and 18 months. Linear mixed effect model will be used, with FC-SRT as the primary outcome and time (in months), treatment (binary indicator) and their interaction as the primary

predictors. The model will include site and APOE-ε4 as categorical covariates and random intercept for participant to account for within-person correlation of FC-SRT scores. As noted above, additional adjustments will be included for participant pre-randomization characteristics (such as age, gender, education level, baseline MMSE or others) that show clinically meaningful differences between treatment arms. This model will be further modified to 1) use time points as four indicator variables rather than a linear term (i.e., 6, 12, and 18 months vs. baseline), 2) include random slope for time as a linear term to account for potential heterogeneity in trajectories across participants. This model will estimate two random effect variances and their covariance, and 3) account for potential correlation of residuals by specifying a covariance structure for residuals. These additional models will be informed by exploratory analysis of outcome distribution over time and will be compared using Bayesian Information Criterion (BIC). Similar longitudinal analyses will be performed for secondary outcomes.

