
only ApoE- ϵ 4 negative patients. The power for the overall sample was based on a type I error of 0.08, while a type I error rate of 0.01 was used for the ApoE- ϵ 4 negative participants. An additional alpha of 0.01 was allocated for the ApoE- ϵ 4 positive patients; however, simulations were not undertaken for this patient population, since there was no preliminary evidence of a treatment effect among the ApoE- ϵ 4 positive patients. Based on these data simulations, we estimate a power of 92.4% to statistically detect a larger FC-SRT slope in the metformin group as compared to the FC-SRT slope among the placebo arm (e.g. 9240 out of 10,000 samples produced a significant interaction model term at the alpha = 0.08 level in the regression analysis). Similarly, we found an estimated power of 97.8% to detect a statistically larger FC-SRT slope in the metformin versus placebo groups among the ApoE- ϵ 4 negative patients at alpha = 0.01 level. The proportion of ApoE- ϵ 4 negative patients ranged from 67% to 79% among the 10,000 simulated samples, as compared to a proportion of 73.8% for the ApoE- ϵ 4 negative patients (59 of 80) in the preliminary study.

Given these power analyses, the study team is confident that the reduction in sample size from 370 to 326 will not compromise the goals of the study.

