9.4 STATISTICAL ANALYSES

9.4.1 GENERAL APPROACH

Exploratory data analysis will be performed on the entire study sample. All variables will be checked for outlying and unusual observations to detect general patterns, identify gaps and inconsistencies in the data. Visual inspection will be performed by means of box plots, scatterplots, quantile plots and others. Outliers will be checked for possible data entry errors. Reported descriptive statistics for continuous variables will include the number of participants with non-missing observations, median, mean, SD, interquartile range and range, while statistics for categorical variables will include the frequency and percentage of participants in each category.

Adjustment for covariates. In the primary analysis, all models described below will be adjusted for, ApoE- ϵ 4 (as a binary indicator), age (continuous), self-reported sex (male or female) (categorical), baseline total recall FC-SRT score (continuous), MMSE score (continuous), BMI (continuous) and HbA1c level. Additional adjustment for site, BMI, gender, race, educational attainment, COVID-19 history, and white matter hyperintensity will be done as sensitivity analyses. Statistical tests will be two-sided.

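### The sensitivity mixed models in 9.4.2.1 treat the baseline score as a response and leave the treatment main effect free, so the treatment-by-time term gains almost no precision from baseline and carries chance baseline imbalance

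*Protocol*

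**What the plan says.** Protocol 9.4.2.1 opens by fixing the role of these models: "The following will be used as sensitivity analyses". The FC-SRT measured at baseline and months 6, 12 and 18 is the response. The predictors are "time (in months), treatment (binary indicator) and their interaction as the primary" terms, with site and APOE-ε4 as covariates and a "random intercept for participant to account for within-person correlation of FC-SRT scores". One variant is to "use time points as four indicator variables rather than a linear term (i.e., 6, 12, and 18 months vs. baseline"; others add a random slope or correlated residuals. Further covariates enter only if they are characteristics "that show clinically meaningful differences between treatment arms". The section extends similar models to the secondary outcomes.

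Two other sections bear on this. Section 9.4.1 says "In the primary analysis, all models described below will be adjusted for" a list that includes "baseline total recall FC-SRT score (continuous"). Section 9.2.2 supports the reduced sample size partly with the power of a treatment-by-time test: "9240 out of 10,000 samples produced a significant interaction model term" at alpha 0.08, that is 92.4%.

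The primary analysis (9.4.2) is a different one: a TMLE that adjusts for baseline variables.

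**The concern.** Randomisation rules out a systematic baseline difference, yet the model spends a parameter on one. With month 0 among the responses and a free treatment main effect, the interaction compares change from baseline between arms and ignores how strongly the baseline score predicts later scores. Two things follow. The standard error is larger than it need be. And if one arm starts lower by chance, regression to the mean enters the estimate.

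These models are the stated check on a primary estimator that does use baseline. If the two differ, part of the difference may reflect only the handling of a chance baseline gap, and the check becomes harder to read. The pilot shows that such gaps occur: metformin started 1.9 SRT points lower (34.2 against 36.1, Table 2).

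**Working it through.** **1. The protocol's own figures.** In 9.2.2 the slope intervals give standard errors (1.13 - 0.56)/3.92 = 0.145 and (0.79 - 0.25)/3.92 = 0.138. The standard error of the difference is √(0.145² + 0.138²) = 0.200, so z = 0.33/0.200 = 1.65 and p = 0.10, as stated. Taking z = 1.645 (p = 0.10) and scaling from 80 to 300 participants, power is Φ(1.645 × √(300/80) - 1.751) = 92.4%, as stated. The 278 is also consistent with the text: d = 0.3, 139 per arm and two-sided 0.10 give 80.4%. At 0.08 this becomes Φ(0.3 × √(139/2) - 1.751) = 77.3%.

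**2. Correlation.** The protocol gives none for the FC-SRT. Table 2 (pilot SRT, baseline to last visit) implies ρ = (s₀² + s₁² - s_change²)/(2 s₀ s₁):
- metformin: (7.9² + 9.1² - 8.5²)/(2 × 7.9 × 9.1) = 0.51
- placebo: (9.5² + 8.4² - 8.7²)/(2 × 9.5 × 8.4) = 0.53
- pooled: 0.52

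**3. Variance ratio, common baseline mean over free main effect** (random intercept, complete data).
- Visit indicators: the free model gives a contrast variance proportional to 2(1 - ρ), the constrained model 1 - ρ². The ratio is (1 + ρ)/2 = 0.76.
- Linear time at 0, 6, 12 and 18: the ratio is 180/(504 - 1296ρ/(1 + 3ρ)) = 0.75.

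**4. Power after the change, visit indicators.** At ρ = 0.52, Φ(2.501/√0.76 - 1.751) = 86.8%, up from 77.3%. Starting from 92.4%, Φ(3.186/√0.76 - 1.751) is about 97%. Applying the ratio to 92.4% is approximate, since that figure comes from a regression with robust standard errors on 12-month pilot data.

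| ρ | Precision lost | Gain from 77.3% (points) | Gain from 92.4% (points) |
|---|---|---|---|
| 0.4 | 30% | 11.9 | 5.6 |
| 0.5 | 25% | 9.9 | 4.9 |
| 0.52 | 24% | 9.5 | 4.7 |
| 0.6 | 20% | 7.9 | 4.1 |
| 0.7 | 15% | 5.9 | 3.2 |
| 0.8 | 10% | 3.9 | 2.2 |

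**5. Random slope.** In four illustrative covariance structures (baseline to month-18 correlation 0.43 to 0.58) the ratio ranged from 0.81 to 0.97, a loss of about 3-20%.

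**6. Imbalance.** Given a baseline gap g, the expected month-18 gap moves by ρg while the change score subtracts all of g, so the estimate shifts by -(1 - ρ)g, or -0.48 per point at ρ = 0.52. With linear time the weights on the four visits are -0.9, -0.3, 0.3 and 0.9, and the shift is -0.9(1 - ρ) = -0.43. In 1,500 simulated trials (ρ = 0.52, 139 per arm, visit indicators) the shift was -0.46 per point under the free model and about 0.02 under either alternative. The variance ratios were 0.77 for both alternatives.

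**7. Baseline as an added covariate.** With complete data and month 0 kept in the response, adding the baseline score left the interaction estimate unchanged to rounding error. With score-dependent dropout (25 simulated trials) it moved the estimate by 0.07 standard errors on average, at most 0.22, and cut the standard error by about 1.6%.

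**The case against.** The strongest answer is that nothing rests on this model. It is labelled a sensitivity analysis, has no alpha of its own, and plays no part in the phase III rule of 9.4.10. The primary TMLE adjusts for baseline. ADCS-PACC and plasma biomarkers follow the primary approach, and imaging uses analysis of covariance (9.4.3). All of this stands. A reader might infer that the primary test or the go/no-go decision loses power; the protocol does not support that.

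Nor is the model wrong. It is a standard form, unbiased under randomisation for the difference in change named in the null hypothesis. A reader might infer bias or a different estimand; the fault is inefficiency and sensitivity to a chance gap, not the target.

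It can be said that 9.4.1 already puts baseline FC-SRT into every model. Its opening words tie the list to the primary analysis, while 9.4.2.1 gives its own covariates. Even on the generous reading, step 7 shows little benefit.

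The size is open to challenge. A flat 25% loss, or nine to ten power points, would be a tempting headline, but it borrows a 12-month correlation from another test with last observation carried forward and assumes a random intercept. From the protocol's 92.4% the gain is about 5 points. The pilot does not give a clean before-and-after illustration either: Table 2's printed changes differ by 9.4 - 5.7 = 3.7, while its means give (43.6 - 41.5) - (34.2 - 36.1) = 4.0.

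Finally, parameterisation is often left to the SAP. Here, however, the protocol states the model form, so the point concerns text that is present.

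**Conclusion.** The point holds as a worthwhile improvement to a supportive analysis, not as an error in the primary inference. As written, the treatment-by-time term gains essentially no precision from the baseline score and carries chance imbalance. Under a random intercept with visit indicators the loss is (1 - ρ)/2: about 24% if the pilot SRT value of 0.52 carries over to the FC-SRT and is equal between visits, and 30% to 10% for ρ from 0.4 to 0.8. It is smaller if participants' slopes vary appreciably. The power equivalent at ρ = 0.52 is about 77% to 87% at the design effect of 0.3, or 92.4% to about 97% from the protocol's own figure. The structural finding does not depend on these values; only its size does.

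**What to change.** In 9.4.2.1, for the FC-SRT and for each longitudinal secondary outcome, choose one of two forms:
- Keep months 0, 6, 12 and 18 as responses but give both arms one baseline mean: time plus treatment-by-visit terms at 6, 12 and 18 months, with no treatment main effect.
- Take months 6, 12 and 18 as responses, with that outcome's own baseline score and its interaction with visit as covariates.

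Name the 18-month contrast as the estimate to set beside the TMLE. State that baseline will not be entered as a covariate while month 0 remains a response, and reconcile the covariate wording of 9.4.1 with that of 9.4.2.1.

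The cost is a sentence or two of text. No new data are needed, and randomisation justifies the common baseline mean.

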9.4.3 ANALYSIS OF THE SECONDARY ENDPOINT(S)

Analytic plan for secondary aims. Our secondary aims compare changes in the ADCS-PACC between metformin and placebo on an ITT basis. The analytic approach will be the same as described for the Primary Aim. This will also apply to outcomes measured at all visits, including the plasma AD biomarkers. We will also compare changes from baseline to 18 months between metformin and placebo in brain cortical thickness, white matter hyperintensity volume, brain amyloid SUVR, and brain tau SUVR. Since these analyses will have only 2 time points, we will use analysis of covariance to compare the mean changes from baseline to 18 months, adjusting for study site and other prespecified covariates in the primary analysis.

9.4.4 SAFETY ANALYSES

The number of SAEs will be tabulated by type for the entire study sample as well as by treatment group. Any treatment group differences in SAEs enumerated for interim analyses will remain blinded to investigators associated with this study. Unmasked results will be made available only during the closed sessions of DSMB meetings.

9.4.5 BASELINE DESCRIPTIVE STATISTICS

Treatment arms will be compared on pre-randomization (baseline) characteristics potentially correlated with outcomes to assess for differences in distributions and, therefore, potential confounding. No inferential statistics will be used.

9.4.6 PLANNED INTERIM ANALYSES

Safety data will be looked at by the DSMB at a specified schedule, which is different from a formal interim analysis for efficacy. There will be no interim analysis for efficacy.

9.4.7 SUB-GROUP ANALYSES

Analyses of primary and secondary outcomes will be stratified by the following baseline participant characteristics: (primary) APOE e4 status and age, gender, race, site, type of MCI (early vs. late), BMI, cognition and metabolic status, as measured by Hb1Ac.

9.4.8 TABULATION OF INDIVIDUAL PARTICIPANT DATA

No individual participant data will be tabulated. Individual level data might be presented to the DSMB in a closed report, at their specific request.

9.4.9 EXPLORATORY ANALYSES

Exploratory analyses will include: sensitivity analyses including and excluding data outliers for which data entry errors were ruled out; exploratory analyses examining different metformin cumulative doses according to the doses tolerated during the study; examination of other outcomes such as functional outcomes and other neuropsychological domains such as executive function.

9.4.10 DECISION TO MOVE TO PHASE III TRIAL

The advantage of phase II/III study design is that it is an adaptive design and can decrease the overall number of participants, time and cost of making the decision about efficacy of the intervention. The decision to move to a phase III trial will be based on the analysis of the unblinded phase II trial data, made by a data monitoring committee independent of the study investigators and the DSMB, and will include at least one biostatistician.

Phase III will not be started until all phase II primary outcome data are analyzed. As noted above, if the primary hypothesis regarding the average treatment effect is rejected either for the entire sample or one of the primary subgroups based on the APOE e4 status, at their respective statistical significance levels, the decision will be made to proceed to the phase III trial.

The decision about the participant eligibility/study population for phase III trial will be based on the average treatment effect in the entire study sample versus the primary subgroups. If a positive treatment effect is observed (i.e., average treatment effect > 0 comparing metformin vs. placebo arm) in the study, no additional exclusions for phase III compared to phase II study population will be implemented. However, this decision might be modified by the independent committee depending on the safety profile among different participant subgroups.

Statistically, the phase II and phase III trials are distinct, i.e., no phase II data will be used in the primary analysis of the phase III trial.

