2.2.7.3. MAP was prepared with a comprehensive consultation with the Trials Innovation Center (TIC) at Johns Hopkins University, one of the three hubs of the NCATS trial innovation network (TIN). In December of 2016 we applied for a consultation with the TIC at JHU-Tufts proposing to conduct a phase III trial of metformin in aMCI. The changes in design from the MetMCI study to the current proposal prompted the recommendation to conduct a phase II/III study instead of a phase III study.¹²⁹ The observation that a minority of participants achieved the maximum dose in the pilot study led us to propose the use of the better tolerated extended release metformin. The observation that there were significant practice effects for both outcomes led us to do repeated testing in the titration period in order to establish a cognitive baseline at the end of titration. The increasing acceptance of early MCI as part of the continuum of prodromal AD^{130,131} led us to extend the study sample to include both early and late MCI. Our finding that the SRT was the outcome that showed a signal led us to choose a related outcome that is more sensitive to early change, the FC-SRT. Given these changes in the design we propose a larger phase II study with an a-priori rule to advance to phase III, instead of directly proposing a phase III study. The advantage of this design is that a phase II/III trial is an adaptive approach that decreases the time, number of participants, and cost needed to make a decision about the efficacy of a treatment.¹²⁹ Although there will participant enrollment will be suspended while the data of the phase II portion is analyzed to make a decision to move to phase III, the design and outcomes of the phase III study will be similar to phase II, allowing inclusion of the phase II participants as part of the analytic sample for the final phase III study.¹²⁹ As part of the TIC consultation, we shared our MetMCI dataset with the statistical team at JHU-Tufts, who replicated our findings and analyzed all data points (the primary MetMCI analysis only compared changes between baseline and 12 months between study arms, using LOCF for missing 12 month data). The differences in all time points for the SRT can be seen in Table 4 (below). The metformin arm had lower total recall at baseline compared with placebo but went on to have better performance at months 3, 6, and 12 compared with placebo, and similar performance at month 9. Both study arms showed improvements in recall, but the improvement was strongest in the metformin group. In order to determine the sample size of for the phase II/III study at the time of the original grant application, the TIC team used the MetMCI data to estimate the initial sample size for MAP ($n=370$, 185 per arm). The approach to the sample size calculation is detailed in section 4.4 (statistical design and power). The

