9 STATISTICAL CONSIDERATIONS

9.1 STATISTICAL HYPOTHESES

Primary efficacy endpoint(s)

The primary aim is to compare changes from baseline to 18 months in verbal memory performance, measured with the Total Recall Score of the Free and Cued Selective Reminding Test (FC-SRT), between the metformin and placebo arms, following an ITT approach. We hypothesize that the metformin arm will demonstrate less decline in the FC-SRT as compared with placebo.

Secondary efficacy endpoint(s):

- Examine global cognitive performance, measured with the Alzheimer's Disease Cooperative Study, Preclinical Alzheimer Cognitive Composite (ADCS-PACC). We hypothesize that the metformin arm will demonstrate less decline or improvement in the ADCS PACC as compared with placebo.
- Examine APOE-ε4 genotype as a modifier of the efficacy of metformin. We hypothesize that the benefit of metformin will be highest among APOE-ε4 carriers.
- Compare changes in neurodegeneration, ascertained as cortical thickness in areas affected by Alzheimer's disease acquired on brain MRI from baseline to 18 months between metformin and placebo. We hypothesize that the metformin arm will show less decrease in cortical thickness at 18 months compared with placebo.
- Compare changes in cerebrovascular disease, ascertained as white matter hyperintensities (WMH) volume on brain MRI, from baseline to 18 months between metformin and placebo. We hypothesize that the metformin arm will show less increase in WMH as compared with the placebo arm.
- Compare changes in whole brain Aβ standardized uptake value ratio (SUVR) and in incident amyloid positivity from baseline to 18 months between the metformin and placebo arms.
- Compare changes in tau SUVR in a composite brain region comprising medial and inferolateral temporal cortex from baseline to 18 months between the metformin and placebo arms.
- Compare changes in plasma AD biomarkers between metformin and placebo.

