9.4.2 ANALYSIS OF THE PRIMARY EFFICACY ENDPOINT(S)

Analytic Plan for the Primary Aim. The primary aim for this study is to compare changes from baseline to 18 months in verbal memory performance, measured with total recall in the FC-SRT, between the metformin and placebo arms. The primary null hypothesis H0 states that there is no difference between metformin and placebo arms on change in total recall in the FC-SRT from baseline to 18 months of follow-up. We will follow the ITT principle in which all randomized participants are analyzed based on the group to which they are randomized regardless of early termination or errors in randomization detected post hoc.

To estimate the average treatment effect, we will use the targeted maximum likelihood estimator (TMLE) of van der Laan and Gruber (2012). This estimator involves adjustment for baseline (i.e., pre-randomization) variables that are correlated with the outcome to improve precision in estimating the average treatment effect for FC-SRT score at 18 months. The estimator also involves adjustment aimed at reducing bias due to informative censoring, that is, participant dropout that may be correlated with the primary outcome. This adjustment for missing outcomes is done through a combination of inverse probability of censoring weights and outcome prediction models. Specifically, the weights and prediction models use the pre-specified baseline variables, study arm, and the post-randomization outcomes at 0, 6, 12, and 18 months. The motivation of this approach is that if the FC-SRT score at a given visit is correlated with the FC-SRT value at the next visit and also with dropout, then adjusting for observed differences in FC-SRT scores for those who dropout versus those who stay on study may reduce bias (under the assumption that censoring is missing at random). This adjustment is implemented by fitting models for dropout as a binary outcome using logistic regression models for the primary outcome based on FC-SRT measured at the previous visit, study arm, and baseline variables.

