As the final step, average FC-SRT score under hypothetical assignment to the active treatment is estimated for each participant at 18 months (regardless of their actual assignment), given their baseline covariates. Similarly, average FC-SRT score under hypothetical assignment to the comparison arm is estimated. The primary analysis estimator of the average treatment effect as a mean difference is defined as the difference between the former and the latter. This analysis will be performed in a software that implements the above estimator: <https://github.com/mrosenblum/RandomizedTrialEnhancedPrecisionEstimator>.

To test the null hypothesis that the average treatment effect equals 0, a Wald statistic will be computed that is equal to the estimator of the average treatment effect divided by its estimated standard error. The standard error will be computed by the non-parametric bootstrap (resampling participants with replacement and recomputing the above estimator), and the 92% confidence interval will be computed using the bias corrected (BC) and accelerated (BCa) method.

Prior to computing the average treatment effect, missing baseline variables will be imputed using the median for continuous-valued variables (such as age and MMSE) and mode for categorical variables (such as site, APOE e4 status, gender, and education level). Intermittent missing outcomes at each time point will be imputed with fitted values from a regression model using all baseline covariates, previous outcomes, and treatment assignment as covariates.

Subpopulation defined by APOE- ϵ 4 genotype. The primary pre-specified subpopulation analysis is in terms of the APOE- ϵ 4 genotype. Two subpopulations will be defined based on the genotype: 1) any APOE- ϵ 4 allele present, i.e. APOE- ϵ 4 positive and 2) no APOE- ϵ 4 allele present, i.e., APOE- ϵ 4 negative). For each of the two subgroups, the above-described estimator will be computed, and the null hypothesis of no difference will be tested at 0.01 level of significance. If any of the three (one for combined population, and one for each of the two subpopulations) primary null hypotheses are rejected at their respective significance levels, the decision will be made to proceed to a phase III trial. COVID-19 history will be explored as a potential modifier of the intervention.

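### The phase III go rule has no direction: rejecting any of three two-sided nulls means proceed, even when the result favours placebo

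*Protocol*

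**What the plan says.** Section 2.2.7.3 presents the design as resting on a rule fixed in advance: "we propose a larger phase II study with an a-priori rule to advance to phase III".

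The rule appears twice. Section 9.4.2 says that if any of the three "primary null hypotheses are rejected at their respective significance levels, the decision will be made to proceed to a phase III trial". Section 9.4.10 repeats that phase III follows "if the primary hypothesis regarding the average treatment effect is rejected either for the entire sample or one of the primary subgroups", each at its own level.

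The tests behind it are non-directional. Section 9.4.1 states: "Statistical tests will be two-sided". In section 9.4.2 the primary null is that "there is no difference between metformin and placebo arms on change in total recall in the FC-SRT", tested by a Wald statistic against an average treatment effect of zero. The levels are 0.08 for the whole sample, with a matching 92% interval, and 0.01 in each APOE-e4 stratum.

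The research hypothesis in section 9.1 does have a direction: "We hypothesize that the metformin arm will demonstrate less decline in the FC-SRT as compared with placebo".

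Section 9.4.10 contains one sign condition, "average treatment effect > 0 comparing metformin vs. placebo arm". It stands in the paragraph on who will be eligible for phase III, and its consequence is that no further exclusions are added. The same paragraph ends by saying that "this decision might be modified by the independent committee depending on the safety profile among different participant subgroups".

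**The concern.** A two-sided test of no difference rejects in both directions. A go rule that depends only on rejection therefore gives the same answer when metformin is significantly better and when it is significantly worse. The protocol states this rule in full and in mandatory terms, so it is not a detail left to the SAP.

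The purpose of an a-priori rule is that the decision after unblinding follows from the text. If the whole sample or one APOE-e4 stratum rejected in favour of placebo and no population rejected for benefit, a committee that sensibly stopped would have to depart from the written rule. A committee that followed the text would launch a phase III trial on evidence of worse memory performance. The rule is also ambiguous when one stratum rejects in favour of placebo while the overall estimate is positive: it says proceed, and the eligibility sentence then says that no exclusions are added.

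**Working it through.** **1. Is the design two-sided as sized?** Section 9.2.2 gives 278 for d = 0.3, with 80% power and an error rate of 0.1 (the alpha and beta labels are swapped in the text). The normal formula, two-sided, is n per arm = 2(z₀.₉₅ + z₀.₈₀)²/d² = 2(1.645 + 0.842)²/0.09 = 137.4, so 138 per arm or 276 in total. The noncentral-t version gives 139 per arm, which is the stated 278. With 10% annual loss over 1.5 years, 278/0.9^1.5 = 325.6, so 326. A one-sided 0.10 test at 80% power needs only 202. The total is therefore a two-sided 0.10 = 0.08 + 0.01 + 0.01.

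**2. Does any sentence supply the direction?**
- Go sentence, 9.4.2: any of three nulls rejected. No sign condition.
- Go sentence, 9.4.10: rejected overall or in one stratum. No sign condition.
- Positive-effect sentence, 9.4.10: governs phase III eligibility. It refers to the effect in the study, not in the population whose null was rejected.
- Committee's power to modify, 9.4.10: attached to eligibility and based on subgroup safety, not on the direction of efficacy.

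None of them makes go conditional on benefit.

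**3. How often would it matter?** The protocol gives no go probability, so this is by simulation (4,000,000 draws per scenario).

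Inputs:
- Analysed n = 278 (9.2.2) and 326 (9.3).
- APOE-e4 non-carriers 60% (9.2.1) or 73.8% (9.2.2), giving non-carriers/carriers of 167/111 and 205/73 (n = 278), and 196/130 and 241/85 (n = 326).
- Stratum estimate normal with mean d and standard error 2/√n for that stratum. The overall estimate is the n-weighted mean.
- Rejection if |z| > 1.751 overall (0.08) or |z| > 2.576 in a stratum (0.01).

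Pilot-like effects come from Table 3 in section 2.2.7: non-carriers (10.7 − 5.9)/pooled SD of 8.2 and 8.6 = 0.57; carriers (5.7 − 5.2)/pooled SD of 9.1 and 9.2 = 0.05. A more cautious 0.4/0.05 was also run.

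| True effect | P(go) as written | Some rejection favours placebo | Go with no rejection for benefit |
|---|---|---|---|
| None | 8.7% | 4.35% | 4.35% |
| d = +0.3 in both strata, n = 278 | 78% | below 0.01% | below 0.01% |
| d = +0.3 in both strata, n = 326 | 83% | below 0.01% | below 0.01% |
| 0.57 / 0.05 | 94 to 99% | 0.2 to 0.3% | 0.01 to 0.03% |
| 0.4 / 0.05 | 71 to 87% | 0.2 to 0.3% | 0.07 to 0.11% |

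The last column is the share of trials in which a direction clause would change the decision. Analytic check on d = +0.3: the overall test alone has shift 0.3 × √(139/2) = 2.50, and Φ(2.50 − 1.75) = 77%. The strata add about half a percentage point.

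**4. Assumed harm, for illustration only.** The pilot does not suggest it. At d = −0.1, −0.2 and −0.3, the rule as written says go on a result favouring placebo in about 19, 47 and 78% of trials (n = 278), or 21, 53 and 83% (n = 326). By symmetry, the d = −0.3 figures equal the power at d = +0.3. With the clause, go falls to about 0.6% or less at d = −0.1 and to below 0.1% at the other two.

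**The case against.** The best defence is that nobody could mistake the intent. Section 9.1 states a directional hypothesis. The power statements in section 9.2.2 describe detecting a larger slope on metformin at the 0.08 and 0.01 levels. Section 9.4.10 opens by calling this a decision about efficacy, and provides an eligibility rule only for a positive effect. An independent committee that includes a biostatistician decides on the unblinded data, and declining to proceed on a placebo-favouring result can only make a false go less likely. On this view the omission is editorial.

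Most of that is true, and it limits the severity. It does not make the rule right. Each of those passages shows what the authors wanted; none is a condition for proceeding. The pre-specified rule is where the direction has to stand.

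Two further objections have some force. First, the harm percentages rest on an assumption and should not drive the rating; they do not. Second, a direction clause leaves go unchanged when one population rejects for benefit and another for placebo. Under the pilot-like scenarios this describes about half or more of the rare trials with any placebo-favouring rejection. Going ahead on the population that benefits is still coherent there. What then needs settling is the phase III population, on which section 9.4.10 is not clear.

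**Conclusion.** The point holds, and should be fixed. As written in sections 9.4.2 and 9.4.10, the rule sends the trial to phase III on a significant result in either direction. With no true effect, half of its go decisions (about 4.35 of 8.7 percentage points) would favour placebo. If metformin performs as in the pilot, the practical consequence is very small, at most about 0.11% of trials. The case for correcting it is that a rule presented as a-priori is wrong as stated and can be corrected at no cost.

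The reading of the text needs no assumption. The sizes assume normally distributed test statistics, equal allocation within strata, 278 to 326 analysed, and 60 to 73.8% non-carriers. They take no account of any precision gain from covariate adjustment.

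**What to change.** In both 9.4.2 and 9.4.10, write the rule as: *proceed if a null is rejected at its level and the corresponding estimate favours metformin*. Repeat it in the SAP, and make the change before unblinding. Two-sided reporting and the 92% interval can stay.

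As a minor accompanying edit, reconcile the two sentences in 9.4.10 on the phase III population: one bases it on the overall effect versus the subgroup effects, the other adds no exclusions whenever the effect in the study is positive. Whether to restrict that population is for the sponsor.

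The cost is one clause in two sections. Sample size and alpha split do not change, and power for benefit at d = 0.3 stays at 78% (n = 278) or 83% (n = 326).
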